### CONSORT 2010 Flow Diagram

## **10.6 Non-Inferiority and Superiority testing**

First, the primary analysis will be performed for non-inferiority in the PP1 population. If the primary analysis rejects the null hypothesis (i.e. CO-CPR is non-inferior to CPR with respect to the primary or some secondary outcomes), the comparisons between the treatment groups will also be done for superiority using 95% two sided confidence interval.(28) Second, the same analysis (first non-inferiority and then superiority) as above will be done for the ITT and PP2 population. The non-inferiority limit 1% will be used for both primary and secondary outcomes.

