## 6. Trial design

This is an interventional, prospective, randomized, 1:1 open label, multicenter trial comparing two different methods of bystander CPR in witnessed cases of OHCA. Since CO-CPR is a simplified form of CPR that could lead to a higher incidence of bystander-CPR by itself a non-inferiority design for the primary outcome has been chosen. Superiority testing will also be performed for the purpose of demonstrating a possible increase in survival with CO-CPR.

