### 6.2 Trial phases and intervention:

#### 6.2.1. Phase 1 and 2: The work at the dispatch center and CPR by bystander

- Identification of cases
- Screening for inclusion and exclusion
- Randomization
- Instructions according to allocation

Suspected OHCA identified at the dispatch centre, classified as unconscious with no or agonal breathing, are eligible for screening. When a dispatcher suspects a case of OHCA, inclusion criteria and exclusion criteria will automatically pop up on their computer screen. The first inclusion criterion is if the collapse is witnessed (has been seen or heard). The second inclusion criterion is if any bystander on the scene has previous CPR-training. According to current guidelines, the dispatch operator asks whether the witness has training in bystander CPR. If not, they are offered instructions on how to perform telephone-guided CPR (T-CPR) and the case is not further screened for inclusion in the study. If any bystander at the scene has previous CPR-training (any time), or if CPR is already on going, the case can be further screened for inclusion in the study. The dispatch operator will mark this on their desktop environment. This automatically triggers the appearance of exclusion criteria on the

operator's desktop: 1) OHCA victim aged 18 or younger? 2) Asphyxia (i.e. drowning, strangulation, hanging 3) intoxication, drug overdose? 4) trauma? or 5) pregnancy?

If any of the exclusion criteria are met, the case is not randomized (and is handled according to standard protocol). If no exclusion criteria are present, the case will undergo randomization using a Microsoft.NET Random Constructor (Int 32). This will generate a randomized allocation to either intervention (CO-CPR) or control (S-CPR). A new pop-up will then appear on the operator's desktop with detailed instructions to the caller in both groups. Simultaneously, the EMS will be dispatched.

The bystander will, in all cases included and randomized, obtain instructions from the dispatcher to provide either CO-CPR or S-CPR until arrival of the EMS.

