#### **6.3. Blinding**

Because of the inherent logistical problems with blinding of CPR techniques for dispatchers, the trial is considered as an “open labeled” trial. Treatment allocation will, however, be blinded in data management and at follow-up, for personnel treating the patients at the hospitals and for all responsible researchers. Allocation concealment will be preserved.

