## 8. Data collection

### From the dispatch organization (SOS-Alarm AB) the following variables will be collected:

Time of incoming call, time of dispatch of EMS, time of dispatch of first responders when applicable, time for screening for inclusion, time of randomization and time of arrival of EMS and first responders. Event times are automatically generated and stored in the dispatch organization's computer system. The randomized assignment for each call is stored in a separate data-file generated by the random sequence constructor.

For evaluation of included calls and adherence to protocol all randomized, EMS treated OHCA dispatch calls will be audited. All audit evaluators will be blinded to allocation. A standardized template for evaluation of dispatcher assisted CPR will be used (cardiac arrest registry to enhance survival – CARES).(25) The study specific inclusion criteria will be added as auxiliary variables (supplementary app).

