## 10.4 Analysis step and strategy of the whole study populations

The target study population is witnessed OHCA of medical origin where any bystander at the scene has previous CPR training. All randomized calls of suspected OHCA will be included.

Patient with previous decision that CPR should not be initiated i.e. terminal illness or palliative care and cases where EMS did not start CPR for other reasons (sure signs of death, not true OHCA) will be excluded from data analysis. The remaining patients will be analyzed in the ITT population.

Blinded call audit will be used to define type of CPR instructions provided. All randomized EMS treated OHCA receiving instructions in accordance with randomized allocation will be treated as the target study population treated per protocol (PP1).

Finally, patients who are randomized but later judged as not fulfilling all criteria for inclusion before randomization, as evaluated by call audit (not witnessed, asphyxic, bystanders with no previous CPR training), will be removed and remaining patients will be analyzed as PP2.

Thus, we perform ITT analysis, PP1 and PP2 analysis based on the following patients:

Intention to treat (ITT) analysis: We define the ITT population as all included and randomized EMS treated OHCA patients that not fulfilled any exclusion criteria's.

Per protocol 1 (PP1): We define the PP population as the subset of the ITT population where the bystanders received the allocated instructions by the dispatch operator, as defined by the call audit.

Per protocol 2 (PP2): We define the PP2 population as the subset of the PP1 population where the patients fulfilled all inclusion criteria, as defined by call audit.

Please see also Consort Diagram in section 10.5.

The reasoning behind excluding patients after randomization is two-folded:

First: Dispatchers suspecting OHCA based on initial information in a phone-call do patient inclusion and randomization. In this situation there is very limited information and dispatchers are encouraged to treat all calls where the patients are not conscious and not breathing normally as suspected OHCA

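### Section 10.6 lets PP1 lead for superiority as well as non-inferiority, and gives no rule for a superiority conclusion when PP1 and ITT disagree

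*Combined protocol and SAP*

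**What the plan says.** Superiority is a declared aim. Section 6 says "Superiority testing will also be performed for the purpose of demonstrating a possible increase in survival with CO-CPR", and Section 10.1 adds that the design allows for it.

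Section 10.6 sets the order: "First, the primary analysis will be performed for non-inferiority in the PP1 population". If that null hypothesis is rejected, "the comparisons between the treatment groups will also be done for superiority using 95% two sided confidence interval". The other two populations follow: "Second, the same analysis (first non-inferiority and then superiority) as above will be done for the ITT and PP2 population". Section 10.5 also sizes the trial on PP1 and calls it the primary analysis. No section says which population decides a superiority conclusion when they differ.

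Section 10.4 defines PP1: "We define the PP population as the subset of the ITT population where the bystanders received the allocated instructions by the dispatch operator". Section 10.5 assumes that 20% will not receive the allocated intervention. It also assumes that 40% of included patients drop out after randomisation because they were not treatable arrests.

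On who knows the allocation: after randomisation a pop-up appears on the operator's "desktop with detailed instructions to the caller in both groups" (Section 6.2.1). Section 6.3 gives the reason for the open label: "Because of the inherent logistical problems with blinding of CPR techniques for dispatchers". Of the call audit that defines PP1, Section 8 says "All audit evaluators will be blinded to allocation".

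**The concern.** PP1 is a defensible lead population for the non-inferiority objective. Superiority is different. Membership of PP1 depends on something that happens after randomisation: which instruction the dispatcher gave, knowing the allocation. If whatever made a dispatcher depart from the allocation (the caller, the patient, the course of the call) is related to survival and acts differently in the two arms, the arms of PP1 are no longer comparable. Blinded auditors protect the classification of what was said on the call, not the dispatcher's decision to say it.

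At stake is a claim that CO-CPR saves more lives. If PP1 and ITT give different answers, the plan gives the authors no rule, so the weight given to each set could be settled after the results are known.

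**Working it through.** **Inputs.** From Sections 10.5 and 10.6: 30-day survival 11% (S-CPR) and 13.1% (CO-CPR); margin 1.0 point; one-sided alpha 2.5%; 1630 per arm in PP1; 20% lost from ITT to PP1; 40% lost from randomised to ITT. Assumed, because the documents do not give it: survival among the patients removed from PP1.

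**The plan's own figures.** 3260/(0.8 × 0.6) = 6791.7, which matches 6792. In PP1 the unpooled standard error is √((0.131×0.869 + 0.11×0.89)/1630) = 0.01140. Non-inferiority power is Φ(0.031/0.01140 − 1.96) = 77.6%, against 80% stated. Superiority power is Φ(0.021/0.01140 − 1.96) = 45.3%; the plan states none.

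**Selection in PP1 when there is no true effect (illustration).** Let q be the share removed in an arm and g the kept-minus-removed difference in survival. With equal ITT survival, the bias in PP1 is q(CO)·g(CO) − q(S)·g(S).
- No selection: false superiority of CO-CPR is 2.5% in PP1 and in ITT.
- 20% removed in each arm; CO-CPR 11.5% kept and 9.0% removed; S-CPR 11% in both. Bias = 0.20×2.5 − 0.20×0 = 0.5 point. SE = √(2×0.11×0.89/1630) = 0.01096. False superiority = Φ(−1.96 + 0.005/0.01096) = 6.6%.
- The same bias reversed: Φ(−1.96 − 0.005/0.01096) = 0.8%.
- Unequal removal, 25% v 15%, with a 5-point gap in both arms: 0.25×5 − 0.15×5 = 0.5 point. Kept survival is 12.25% of 1528 v 11.75% of 1732, SE = 0.01141, false superiority 6.4%.

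In all of these ITT stays at 2.5% because the example sets its true difference to zero. That is a premise, not a result.

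**How often the two sets disagree at the planning rates.** ITT has 3260/0.8/2 = 2037.5 per arm. Three assumptions about the removed 20% were used: they take on the other arm's survival (full crossover), have the same survival in both arms (no contrast), or keep the full effect. Powers are analytic. Disagreement is by simulation: 2,000,000 trials per case (1,000,000 for the last column), 1630 kept and 407 removed per arm, unpooled 95% interval.

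| Removed patients | ITT survival, CO v S | ITT superiority power | PP1 superior, ITT not | ITT superior, PP1 not |
|---|---|---|---|---|
| Full crossover | 12.68% v 11.42% | 23% | 23% | 0.8% |
| No contrast | 12.89% v 11.21% | 38% | 12% | 4% |
| Full effect kept | 13.1% v 11% | 54% | 4% | 12% |

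With no effect and no selection, each kind of disagreement occurs in about 1% of trials. In the three table rows CO-CPR truly is better, so those disagreements are not errors. They show how often a rule would be needed.

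**The case against.** The primary objective is non-inferiority, and superiority is an addition with no stated power. The ITT superiority analysis is already planned. The audit is blinded. Section 10.5 foresees departures in both directions, so bias need not favour CO-CPR. The 6.6% rests on an invented survival gap, and the reverse case is conservative. ITT is itself selected: it drops an assumed 40% according to whether EMS started CPR, which is decided after the instruction was given.

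All of this is correct, and it limits the point. A reader might infer four stronger things that the documents do not support:
- **That no population leads.** PP1 leads by label (Section 10.5) and by order (Section 10.6). What is missing is a rule for disagreement.
- **That PP1 is biased towards CO-CPR.** Removal by arm and survival among those removed are not given.
- **That PP1 always finds superiority more readily than ITT.** If the removed patients keep the full effect, disagreement in favour of ITT is about three times as frequent (12% v 4%).
- **That membership of the ITT population is unsettled.** Section 10.4 largely settles it. Prior decisions against CPR and cases where EMS did not start CPR are excluded and the rest are ITT; failures of inclusion criteria found later by audit are removed only for PP2.

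What the objection does not answer is that the lead set for superiority is chosen by an unblinded action after randomisation, and that nothing tells the authors what to conclude if ITT differs.

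**Conclusion.** The point stands and should be fixed before the allocation code is broken. It concerns the superiority claim only; the PP1 non-inferiority test is not in question. Section 10.6 gives the superiority lead to the more selected of two planned populations and has no rule for disagreement. At the planning rates the two sets would disagree on superiority in about 16% to 23% of trials (adding the last two columns of the table), depending on the assumption about removed patients. The error rates of 6.6%, 6.4% and 0.8% depend wholly on assumed selection. They show that the 95% interval in PP1 does not protect against it, not that it is present. ITT is less selected than PP1, because it does not condition on the instruction given, but it is not free of selection. It also matches the objective in Section 4.1, which concerns instructions to perform CO-CPR.

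**What to change.** In Section 10.6:
1. Keep PP1 primary for non-inferiority.
2. Base any superiority conclusion on the planned ITT population (all randomised EMS-treated OHCA, as Section 10.4 describes), with PP1 and PP2 supportive.
3. Require that any disagreement between PP1 and ITT be stated in the conclusion.

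Section 10.1 already plans a Consort diagram. It should show the losses from randomised to ITT and from ITT to PP1 by arm and reason, if it does not already do so; the figure could not be seen in the text reviewed.

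The cost is SAP wording and possibly a fuller diagram, since the ITT analyses are planned. The downside is superiority power of 23%, 38% or 54% in ITT under the three assumptions, against 45% in PP1. As the plan states no superiority power, no stated target is missed. Sample size and the PP1 non-inferiority test are unchanged. ITT non-inferiority should be reported as planned but not made a second hurdle: on the same three assumptions its power would be Φ((d + 0.01)/SE − 1.96) = 60%, 75% or 86%, where d is the ITT difference in the table and SE is about 0.0102.

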### 4.1 Primary objective

To evaluate whether survival to 30 days following instructions to perform CO-CPR is non-inferior compared to instructions to perform S-CPR to bystanders with prior CPR training in witnessed OHCA.

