### 4.2 Secondary objectives

To evaluate whether there is a difference between CO-CPR and S-CPR in survival to hospital admission, neurological favorable survival, defined as survival with cerebral performance category (CPC) 1-2, neurologically intact survival defined as CPC 1 and long-term survival, defined as survival to one year. To evaluate whether there is a difference between CO-CPR and S-CPR in VT/VF as first rhythm and Return of Spontaneous Circulation (ROSC). To compare 30-day survival between CO-CPR and S-CPR in pre specified subgroups.

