## 10. Data analytic and statistical analysis plan (SAP)

### 10.1 General statistical analysis plan

This trial is designed to investigate whether CO-CPR is no worse than S-CPR using a non-inferiority design. It has also been designed for the possible of a superiority testing. This statistical design has been chosen appropriately judged on the presumption that CO-CPR has potential clinical benefit but also is easier to perform (and therefore would lead to a higher number of patients receiving the treatment). The largest difference in 30-day survival (primary outcome) that is considered clinically relevant is 1.0 percentage point (please see also section 9.3).

Eligibility, allocation, inclusion and exclusion will be displayed in a Consort diagram. Differences in proportions between baseline characteristics and outcome will be tested by Fisher exact test. Differences in mean or medians between the treatment groups will be tested by either Student's t-test or Mann Whitney U test depending on distribution. Normality assumptions will be assessed with Kolmogorov Smirnov – test. The estimated between group differences will be presented as proportions and 95% confidence intervals (CI), which will be calculated by the asymptotic method without continuity correction. P-values below 0,05 will be considered statistically significant. Main results will be reported as proportions.

In addition, comparisons between the treatment groups (CO-CPR vs CPR) with respect to the outcomes will be adjusted for background characteristics factors through Binary logistic regression to adjust for possible imbalances due to randomization between the treatment groups. The association between treatment and primary outcome will be presented as odds ratios and corresponding 95% CI intervals. Statisticians at Karolinska Institutet will be responsible for the statistical analysis.

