### 10.2 Statistical hypothesis for non-inferiority

#### 10.2.1 Null hypothesis:

The percentage in 30-day survival for those on the standard treatment instruction CPR is better (higher) than the percentage for those on instruction CO-CPR by an amount of 1.0-percentage units.

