#### 10.2.2 Alternative hypothesis:

The percentage in 30-day survival for those on instruction CO-CPR is better than the standard treatment instruction CPR or only slightly worse (by no more than 1.0 percentage unit). We will call instruction of CO-CPR non-inferior to instruction of S-CPR with respect to 30-day survival if the null hypothesis is rejected.

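### Section 10.6 lets a secondary outcome count as rejection of a null hypothesis that Section 10.2 defines on 30-day survival alone (minor wording error)

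*Combined protocol and SAP*

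**What the plan says.** **Section 10.2.** The null is that 30-day survival under S-CPR instructions exceeds that under CO-CPR instructions by 1.0 percentage point. Section 10.2.2 says what rejection means: CO-CPR is called "non-inferior to instruction of S-CPR with respect to 30-day survival if the null hypothesis is rejected". No other null hypothesis is written anywhere in the document.

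**Sections that agree with 10.2.** The primary objective in Section 4.1 is "To evaluate whether survival to 30 days following instructions to perform CO-CPR is non-inferior compared to instructions to perform S-CPR". Section 6 says "a non-inferiority design for the primary outcome has been chosen". Section 10.1 ties the margin to the same outcome: "The largest difference in 30-day survival (primary outcome) that is considered clinically relevant is 1.0 percentage point". Section 10.5 sizes the trial on 30-day survival in PP1.

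**Section 10.6.** Superiority testing follows "If the primary analysis rejects the null hypothesis". A parenthesis opening with 'i.e.' then restates that condition: "CO-CPR is non-inferior to CPR with respect to the primary or some secondary outcomes". The same section applies the 1% limit to secondary as well as primary outcomes.

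**Secondary outcomes.** Section 6.4.2 lists four: survival to hospital admission, 1-year survival, CPC 1-2 and CPC 1. Section 4.2 words the aim as a difference, not as non-inferiority: "To evaluate whether there is a difference between CO-CPR and S-CPR in survival to hospital admission".

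**The concern.** A result on hospital admission or CPC cannot reject a hypothesis about 30-day survival. The main clause in Section 10.6 and its parenthesis are therefore two different rules. The parenthesis also does not say which secondary outcomes count, or how many are meant by *some*.

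The case that matters is a trial in which 30-day survival misses the margin while one or more secondary outcomes meet it. Under Section 10.2 the null stands. Under the parenthesis it is rejected and superiority testing opens. A report could then cite the plan for saying that the null hypothesis was rejected when the primary comparison had failed. The text leaves the choice between the two rules open until that result is known.

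**Working it through.** **Inputs from the plan.** 1630 per arm in PP1, S-CPR 11% and CO-CPR 13.1%, one-sided 2.5% (Section 10.5); margin 1 point for all outcomes (Section 10.6); asymptotic 95% CI without continuity correction (Section 10.1); one primary and four secondary outcomes (Section 6.4).

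**Assumed inputs.** The documents give no secondary rates. Base control rates: admission 30%, 1-year survival 10%, CPC 1-2 9.5%, CPC 1 7.5%. Outcomes are nested: CPC 1 within CPC 1-2 within 30-day survival within admission, and 1-year within 30-day survival. Deaths between day 30 and one year fall either in the worst CPC group first or in proportion; each range below spans these two rules.

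**Decision rules.** With d the difference in proportions (CO-CPR minus S-CPR) and SE = √[pC(1−pC)/n + pT(1−pT)/n], the lower limit is L = d − 1.96·SE. Non-inferior if L > −0.01; superior if L > 0.

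**Step 1: the plan's own test.** At 11% v 13.1%, SE = √[(0.0979 + 0.1138)/1630] = 0.0114, and power = Φ(0.031/0.0114 − 1.96) = 77.6%, against the stated 80%. That gap is a separate matter and does not bear on this point. With a true deficit of 1.0 point, the simulated 30-day test rejects in 2.5% of trials, as planned.

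**Step 2: 30-day superiority.** L > 0 implies L > −0.01, so superiority on an outcome always carries non-inferiority on it. Trials superior but not non-inferior on 30-day survival: 0.0%.

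**Step 3: how often the two rules part** (400,000 simulated trials per scenario, base rates).

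| Truth on all five outcomes | Event | Any one secondary suffices | At least two needed |
|---|---|---|---|
| 1.0 point worse | null called rejected (2.5% under Section 10.2) | 6.5% to 6.8% | 3.3% to 3.4% |
| 1.0 point worse | primary fails, null called rejected | 4.0% to 4.3% | 0.7% to 0.9% |
| No difference | the rules disagree | 14.4% to 15.5% | about 4.8% |
| 2.1 points better | the rules disagree | 15.0% to 15.6% | 8.4% to 9.2% |

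Over six sets of assumed rates, the first row runs from 5.4% to 8.6% (any one) and from 2.8% to 3.7% (two). Five independent outcomes would give 1 − 0.975⁵ = 11.9%, but nested outcomes are far from independent. The last two rows are disagreements between rules, not false positives.

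**Step 4: the harmful event.** This is a failed primary followed by a false superiority claim on a secondary outcome. At a true 1-point deficit it occurs in about 0.4% of trials (0.2% to 0.5% over the six sets); with no true effect, in about 1.3% at base rates. A hand check shows why it is rare. For admission at 30% v 29%, SE = √[(0.2100 + 0.2059)/1630] = 0.0160. False superiority needs a deviation of 1.96 + 0.0100/0.0160 = 2.59 standard errors, a probability of about 0.5% even before the primary is required to fail.

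**The case against.** The strongest defence is that Section 10.6 plausibly intends outcome-by-outcome testing. A 1% limit for secondary outcomes has little purpose unless each is tested for non-inferiority, and the section gives the order as non-inferiority first, superiority second. On that reading *some* means whichever outcomes pass, and by Step 2 the gate changes no superiority result. The sections that name 30-day survival describe the primary objective and never say *only*. Sections 6.3 and 12 also keep researchers blinded, use an independent statistician and have the manuscript prepared before the code is broken, which narrows the room for a convenient choice.

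Most of this stands. It makes the probable intent clear and the practical harm small. It does not rescue the sentence: the parenthesis equates rejection of the single stated null with a secondary result, and outcome-by-outcome testing is nowhere stated. Blinding limits who can exploit the gap, but it does not say which rule applies.

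Two stronger readings are tempting. A reader might infer that the error rate of the primary test rises to between 6.5% and 11.9%. It does not: Section 10.2.2 still governs the 30-day conclusion, and that test stays at 2.5%. A reader might also infer that the secondary non-inferiority tests should be withdrawn. The documents do not require that, because the 1% limit is prespecified for those outcomes. Calling all of them supportive in every case would be partly a matter of preference.

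**Conclusion.** The sentence is wrong as written, and the error is minor. Sections 10.2 and 10.6 conflict on whether the null is rejected when 30-day survival fails and a secondary outcome passes. The conflict is textual and needs no assumption. Its frequency does: the 6.5% to 6.8% (or about 3.3%) rests on assumed secondary rates and on every outcome lying exactly at the margin, and it counts null-rejected labels, not false clinical claims. The false claims that could follow are about 0.4% at that deficit and about 1.3% with no true effect. The primary error rate and any 30-day superiority claim are untouched.

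**What to change.** In Section 10.6, delete *or some secondary outcomes* so that the parenthesis reads *with respect to the primary outcome, 30-day survival*. State that only non-inferiority on 30-day survival in PP1 rejects the null of Section 10.2.

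For the secondary outcomes, keep the 1% limit and add that:
- non-inferiority and then superiority are assessed on the same outcome;
- a secondary result never counts as rejection of the 30-day null;
- because there is no multiplicity control, these results are read as supportive if 30-day survival fails.

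The cost is a few sentences in the SAP, with no change to sample size or data collection. The downside is that no confirmatory secondary claim is available when the primary fails. At the assumed base rates and the plan's 11% v 13.1%, a secondary superiority claim would lose confirmatory standing in about 3% of trials if every outcome gains 2.1 points (1.2% to 12% over the six rate sets). If every outcome gains in the ratio 13.1/11, the figure is about 18% (9% to 22%), mostly on hospital admission. Those results would still be reported.
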